8.2.6 Preparation
No preparation is required.

8.2.7 Route of administration for this study
Oral (by mouth)

8.2.8 Incompatibilities: Refer to Appendix A1 for a list of general drugs that should be avoided with pazopanib.

In vitro studies suggested that the oxidative metabolism of pazopanib in human liver microsomes is mediated primarily by CYP3A4, with minor contributions from CYP1A2 and CYP2C8. Therefore, inhibitors and inducers of CYP3A4 may alter the metabolism of pazopanib.

Agents that may Increase pazopanib Blood Concentrations

CYP3A4 Inhibitors: Co-administration of pazopanib with strong inhibitors of the CYP3A4 family (e.g., ketoconazole, itraconazole, clarithromycin, atazanavir, indinavir, nefazodone, nelfinavir, ritonavir, saquinavir, telithromycin, voriconazole) may increase pazopanib concentrations. Grapefruit juice may also increase plasma concentrations of pazopanib. Administration of 1500 mg lapatinib a substrate and weak inhibitor of CYP3A4, Pgp and BCRP with 800 mg pazopanib resulted in an approximately 50 % to 60 % increase in mean pazopanib AUC(0-24) and Cmax compared to administration of 800 mg pazopanib alone. Co-administration of pazopanib with a CYP3A4, Pgp, and BCRP inhibitor, such as lapatinib, will result in an increase in plasma pazopanib concentrations. Combination with strong CYP3A4 inhibitors should therefore be avoided, or selection of an alternate concomitant medication with no or minimal potential to inhibit CYP3A4 is recommended. A dose reduction of pazopanib should be considered when it must be coadministered with strong CYP3A4 inhibitors (see Dosage and Administration).

Agents that may Decrease pazopanib Blood Concentrations

CYP3A4 Inducers: CYP3A4 inducers such as rifampin may decrease plasma pazopanib concentrations. Selection of an alternate concomitant medication with no or minimal enzyme induction potential is recommended.

Effects of Pazopanib on CYP Substrates

In vitro studies with human liver microsomes showed that pazopanib inhibited CYP enzymes 1A2, 3A4, 2B6, 2C8, 2C9, 2C19, and 2E1. Potential induction of human CYP3A4 was demonstrated in an in vitro human PXR assay. Clinical pharmacology studies, using pazopanib 800 mg once daily, have demonstrated that pazopanib does not have a clinically relevant effect on the pharmacokinetics of caffeine (CYP1A2 probe substrate), warfarin (CYP2C9 probe substrate), or omeprazole (CYP2C19 probe substrate) in cancer patients. Pazopanib resulted in an increase of approximately 30 % in the mean AUC and Cmax of midazolam (CYP3A4 probe substrate) and increases of 33% to 64% in the ratio of

dextromethorphan to dextrorphan concentrations in the urine after oral administration of dextromethorphan (CYP2D6 probe substrate). Co-administration of pazopanib 800 mg once daily and paclitaxel 80 mg/m² (CYP3A4 and CYP2C8 substrate) once weekly resulted in a mean increase of 26 % and 31 % in paclitaxel AUC and C_{max}, respectively.

Effects of Pazopanib on Other Enzymes and Transporters

In vitro studies also showed that pazopanib is a potent inhibitor of UGT1A1 and OATP1B1 with IC₅₀ of 1.2 and 0.79 μM respectively. Pazopanib may increase concentrations of drugs primarily eliminated through UGT1A1 and OATP1B1.

Effect of concomitant use of Pazopanib and Simvastatin

Concomitant use of pazopanib and simvastatin increases the incidence of ALT elevations. Across monotherapy studies with pazopanib, ALT > 3x ULN was reported in 126/895 (14%) of patients who did not use statins, compared with 11/41 (27%) of patients who had concomitant use of simvastatin (p= 0.038). If a patient receiving concomitant simvastatin develops ALT elevations, follow guidelines for pazopanib posology and discontinue simvastatin. Insufficient data are available to assess the risk of concomitant administration of alternative statins and pazopanib.

Effect of proton pump inhibitors and gastric pH on Pazopanib

Administration of pazopanib with a proton pump inhibitor (PPI) results in a 40% reduction in AUC and time to C_{max} of pazopanib. Therefore, proton pump inhibitors should be avoided with pazopanib. Drugs that raise gastric pH should also be avoided. If such drugs are needed, short acting antacids should be considered in place of PPIs and H₂ receptor antagonists. Separate antacid and pazopanib dosing by several hours to avoid reduction in pazopanib exposure.

Effect of Food on Pazopanib

Administration of pazopanib with a high-fat or low-fat meal results in an approximately 2-fold increase in AUC and C_{max}. Therefore, pazopanib should be administered at least 1 hour before or 2 hours after a meal.

8.2.9 Availability & Supply: Please complete the drug order form located on the protocol page in NOTIS. This form includes directions for ordering.

Currently all sites are using Pazopanib clinical supply that is provided by GlaxoSmithKline (GSK). As each site exhausts this supply, sites will transition to commercial Pazopanib supply provided by Novartis.

As of March 2016 Votrient (Pazopanib) commercial supply with auxiliary label will also be available for the study, provided by Novartis. This commercial supply study drug should be administered and stored according to the instructions specified on the drug labels. There is no set date when commercial supply will take over the clinical supply. It will depend on when the clinical supply is exhausted at each site.

8.2.10 Side effects

Please refer to current IB for details and a complete list of side-effects.

8.2.11 Nursing implications

- Therapy with pazopanib may result in hepatobiliary laboratory abnormalities. Monitor serum liver tests (ALT, AST, and bilirubin) prior to initiation of pazopanib and at Weeks 3, 5, 7, and 9. Thereafter, monitor at Month 3 and at Month 4, and as clinically indicated. Inform patients that they should report signs and symptoms of liver dysfunction to their healthcare provider right away.

- Prolonged QT intervals and torsades de pointes have been observed. Patients should be advised that ECG monitoring may be performed. Patients should be advised to inform their physicians of concomitant medications.
- Cardiac dysfunction (such as CHF and LVEF decrease) has been observed in patients at risk (e.g., prior anthracycline therapy) particularly in association with development or worsening of hypertension. Patients should be advised to report hypertension or signs and symptoms of congestive heart failure.
- Serious hemorrhagic events have been reported. Patients should be advised to report unusual bleeding.
- Arterial thrombotic events have been reported. Patients should be advised to report signs or symptoms of an arterial thrombosis.
- Reports of pneumothorax and venous thromboembolic events including pulmonary embolus have been reported. Patients should be advised to report if new onset of dyspnea, chest pain, or localized limb edema occurs.
- Advise patients to inform their doctor if they have worsening of neurological function consistent with RPLS (headache, seizure, lethargy, confusion, blindness, and other visual and neurologic disturbances).
- Hypertension and hypertensive crisis have been reported. Patients should be advised to monitor blood pressure early in the course of therapy and frequently thereafter and report increases of blood pressure or symptoms such as blurred vision, confusion, severe headache, or nausea and vomiting.
- GI perforation or fistula has occurred. Advise patients to report signs and symptoms of a GI perforation or fistula.
- VEGFR inhibitors such as pazopanib may impair wound healing. Advise patients to stop pazopanib at least 7 days prior to a scheduled surgery.
- Hypothyroidism and proteinuria have been reported. Advise patients that thyroid function testing and urinalysis will be performed during treatment.
- Serious infections including some with fatal outcomes have been reported. Advise patients to promptly report any signs or symptoms of infection.
- Women of childbearing potential should be advised of the potential hazard to the fetus and to avoid becoming pregnant.
- Gastrointestinal adverse reactions such as diarrhea, nausea, and vomiting have been reported with pazopanib. Patients should be advised how to manage diarrhea and to notify their healthcare provider if moderate to severe diarrhea occurs.
- Patients should be advised to inform their healthcare providers of all concomitant medications, vitamins, or dietary and herbal supplements.
- Patients should be advised that depigmentation of the hair or skin may occur during treatment with pazopanib.
- Patients should be advised to take pazopanib without food (at least 1 hour before or 2 hours after a meal).

8.2.12 Return and Retention of Study Drug: Unused or defective drug will be destroyed. Sponsor Novartis should be notified of this action.

9.0 CORRELATIVES/SPECIAL STUDIES

For Cohort 1 and 3:

Cell-free circulating tumor DNA (ctDNA) will be analyzed using the CAPP-Seq method [1,2], a targeted hybrid capture-based NGS method, or the commercial version of CAPP-Seq called AVENIO [3]. Hybrid capture-based NGS was recently developed to improve the detection of multiple cancer mutations with high sensitivity and without significant prior knowledge of the alterations [4–6]. In this “hybrid capture” approach, relevant DNA sequences are hybridized to biotinylated probes [1]. Biotin is bound to streptavidin beads and then unbound DNA is washed away to “pull down” the bait DNA for NGS analysis [1]. Using this principle, Newman and Bratman et al. implemented an ultrasensitive ctDNA detection technique called Cancer Personalized Profiling by Deep Sequencing (CAPP-Seq) [1]. Recurrently mutated genomic regions in the population of a given cancer type are identified through bioinformatic analysis of cancer WES and/or WGS data from databases such as The Cancer Genome Atlas (TCGA) and Catalog of Somatic Mutations in Cancer (COSMIC) [1]. Biotinylated probes are designed against these recurrently mutated regions, and are referred to collectively as the “Selector” [1]. The “Selector” is applied to cell-free DNA from cancer patients, which is followed by NGS in order to quantitate ctDNA with a detection limit of ~0.01% [1,5]. The detection limit was significantly improved to ~0.001% when a NGS error-correction strategy called integrative digital error suppression (IDES) was implemented [2]. This strategy utilized UMIs to reduce the effect of PCR errors and a bioinformatic error correction step called “polishing” to reduce the effect of stereotypical background artifacts [2].

For this project, we will be applying CAPP-Seq to blood and tissue as we have done previously [1,2,7], by isolating DNA from ~10 mL of plasma, inputting ~32 ng into the CAPP-Seq library preparation protocol which starts with adapter ligation, performing PCR, then targeted hybrid capture, and then NGS on a NovaSeq, HiSeq4000 or a NextSeq. We then will analyze the results using the CAPP-Seq or AVENIO bioinformatics pipeline which enables variant-calling and calculation of variant allele fractions (VAFs) which are averaged at each time point to yield the mean VAF. We will use this measure, as well as the ctDNA concentration (VAF x cfDNA concentration) to quantify ctDNA at each time point, and correlate these results with demographic, diagnostic, treatment, and outcomes data.

For Cohort 2:

Sleijfer et al. recently published a translational study in which they evaluated whether cytokine levels in the patients enrolled in EORTC 62043, the phase II study of pazopanib in soft tissue sarcoma, correlated with PFR and OS. They measured levels of several cytokines at baseline and 12 weeks after beginning pazopanib therapy and demonstrated that baseline levels were not predictive, but that high sVEGFR2 and low PIGF were associated with a more favorable PFR at 12 weeks (OR 0.636, 95% CI 0.413-0.977, P=0.039) and (OR 1.081, 95% CI 1.007-1.160, P=0.0318) respectively. There was also a trend toward high sVEGFR2 at week 12 and increased OS and a statistically significant association between low PIGF levels at week 12 and longer OS (HR 1.061, 95% CI 1.025-1.099, P=0.0009) 6.

We propose to measure sVEGFR2 and PIGF levels in blood to both verify the results of Sleijfer et al and to determine if there is an even earlier correlation that can be detected between levels of these cytokines and PFR as well as OS which may allow us to better predict treatment response early on in therapy.

9.1 Sample Collection Guidelines (please see the lab manual for full details)

Mandatory whole blood samples will be collected at screening or predose on Cycle 1 Day 1, and day 1 of Cycles 2, 3, and 4. Approximately 20 ml of anticoagulated whole blood will be collected in 2 EDTA purple top tubes and 1 SST red top tube at each timepoint. Whole blood for DNA, mononucleated cells, and serum should be immediately prepared from the 2 EDTA purple top tubes and SST red top tube, respectively, and frozen down to -80° C prior to shipment using standard laboratory techniques. Samples should be labeled with the corresponding patient's study ID number, initials, and date of collection.

9.2 Sample Processing, Storage, and Shipment

Prepared, frozen blood samples should be shipped on dry ice to the [name] Lab at Washington University (see address below). Samples may be sent in batches approximately every 2 months. Once received, specimens will be processed in the Tissue Core Procurement Facility at Washington University to store nucleated blood cells, DNA, and serum for potential future molecular biomarker studies.

Blood samples for correlative study should be sent to the following address:

Oncology – [name] lab
[name]
[name]
[name]

9.1 Sample Collection Guidelines (please see the lab manual for full details)

Mandatory whole blood samples will be collected at screening or predose on Cycle 1 Day 1, and day 1 of Cycles 2, 3, and 4. Approximately 20 ml of anticoagulated whole blood will be collected in 2 EDTA purple top tubes and 1 SST red top tube at each timepoint. Whole blood for DNA, mononucleated cells, and serum should be immediately prepared from the 2 EDTA purple top tubes and SST red top tube, respectively, and frozen down to -80° C prior to shipment using standard laboratory techniques. Samples should be labeled with the corresponding patient's study ID number, initials, and date of collection.

9.2 Sample Processing, Storage, and Shipment

Prepared, frozen blood samples should be shipped on dry ice to the [name] Lab at Washington University (see address below). Samples may be sent in batches approximately every 2 months. Once received, specimens will be processed in the Tissue Core Procurement Facility at Washington University to store nucleated blood cells, DNA, and serum for potential future molecular biomarker studies.

Blood samples for correlative study should be sent to the following address:

Oncology – [name] lab
[name]
[name]
[name]

10.0 STATISTICAL CONSIDERATIONS

10.1 Study Design/Study Endpoints

This is a single arm two-stage Simon optimum Phase II study of pazopanib and topotecan with progression-free rate at 12 weeks as the primary outcome. The historic PD free rate at 12 weeks for single agent pazopanib is 55%. To detect a 20% improvement (an 11% absolute improvement) with the combination of pazopanib and topotecan in a single-arm two-stage optimum design and a one-tailed exact binomial p- value, a total of 92 evaluable STS patients is required to detect 55% vs 66% with 80%

power and an alpha level of 10%. If 32 out of the first 55 patients are alive and progression free at 12 weeks, the trial may enroll up to 108 patients in order to acquire a total of 92 evaluable patients. At that time, if 56 or more out of 92 are alive and progression-free at 12 weeks, then the trial will conclude that the true 12 week PFS rate is at least 66%. There is a 63% probability of terminating the study after the first stage when the true rate is 55%. See sections 6.0 and 7.0 for definitions of evaluable patients for response and adverse event information.

Osteosarcoma/Liposarcoma exploratory group:

Up to 36 patients with osteosarcoma and 20 patients with liposarcoma will be enrolled to obtain exploratory information for patients with these two histologies. Although the sample sizes in these two cohorts were selected for feasibility rather than to power a specific hypothesis, 56 subjects will provide estimates of PFR and OS with sufficient precision to support additional study of pazopanib in these patients.

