| Study Design | 
Multicenter, phase II trial designed to estimate progression-free rate at week 12 of combination pazopanib and topotecan in patients with soft tissue sarcoma (STS), as well as provide preliminary evidence of benefit for patients with osteosarcoma or liposarcoma.
 
This is a single arm two-stage Simon optimum Phase II study of pazopanib and topotecan with progression-free rate at 12 weeks as the primary outcome. The historic PD free rate at 12 weeks for single agent pazopanib is 55%. To detect a 20% improvement (an 11% absolute improvement) with the combination of pazopanib and topotecan in a single-arm two-stage optimum design and a one-tailed exact binomial p-value, a total of 92 evaluable patients is required to detect 55% vs 66% with 80% power and an alpha level of 10%. If 32 out of the first 55 patients are alive and progression free at 12 weeks, the trial may enroll up to 108 patients in order to acquire a total of 92 evaluable patients. At that time, if 56 or more out of 92 are alive and progression-free at 12 weeks, then the trial will conclude that the true 12 week PFS rate is at least 66%. There is a 63% probability of terminating the study after the first stage when the true rate is 55%.
 
Up to 36 patients with osteosarcoma and 20 patients with liposarcoma will be enrolled to obtain exploratory information for patients with these two histologies.
 
The DSMC reviewed the interim analysis data on 1/11/2017, and has approved cohort 1 to reopen to 96 total patients (to obtain 92 evaluable patients). In addition, based on the percentage of non-evaluable patients during the interim analysis, it was determined that a total of 108 patients would most likely need to be enrolled in order to obtain 92 evaluable patients.
 
The remaining slots have been equally divided in 5 ways among the sites, with an expiration date of May 12, 2017. Status of accrual will be reassessed at that time, and the remaining slots will be divided accordingly.
 |
| Study Center(s) | 
Lead Institution: Robert H. Lurie Comprehensive Cancer Center of Northwestern University
 
Participating Sites: University of Wisconsin, Mayo Clinic (Rochester, MN), Mayo Clinic (Phoenix, AZ), Mayo Clinic (Jacksonville, FL), Washington University, University of Minnesota, University of Iowa
 |

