1.3 Pazopanib in Sarcoma

Pazopanib, a synthetic indazolyl pyrimidine, is a multi-kinase inhibitor of VEGFR-1/2/3, and to a lesser degree PDGFR- α/β , FGFR-1/2, and c-Kit.⁴⁴⁻⁴⁶ In vivo studies showed dose-dependent tumor growth inhibition in a variety of tumor xenografts by pazopanib (colon, melanoma, prostate, renal, breast, lung).⁴⁷ Pazopanib is thought to inhibit angiogenesis through attenuation of VEGFR-2 signaling. Pharmacokinetic analysis revealed that the steady-state concentration (C_{trough}) for tumor growth inhibition in vivo was almost equivalent to the concentration required for in vivo inhibition of VEGFR-2 phosphorylation.⁴⁷

Phase I studies determined Pazopanib 800mg daily as the recommended monotherapy dose.⁴⁸ There is now plentiful evidence that single agent pazopanib has clinical benefit in advanced sarcomas. The phase II study (VEG20002) evaluated single agent pazopanib in patients with relapsed or refractory soft tissue sarcoma.⁴³ Treatment response data are available for 138 patients who received pazopanib 800 mg once daily. Ninety-nine percent of patients had received prior chemotherapy: 35 patients (25%) had received therapy in a (neo)-adjuvant setting, 83 (59%) had received therapy in an advanced setting, and 22 (16%) had received both. The primary endpoint was the progression-free rate, using Response Evaluation Criteria in Solid Tumors (RECIST) at 12 weeks after start of treatment. Patients with leiomyosarcoma, synovial sarcoma and “the other types of sarcoma” strata receiving pazopanib in VEG20002 experienced a 12 week progression free survival rate of \geq 40%, the pre-defined threshold indicating anti-tumor activity. The liposarcoma stratum did not meet its prespecified endpoint at the end of stage 1 and did not progress to stage 2.

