Based on the results of the VEG20002, a Phase III randomized, double blind, placebo controlled study (VEG110727) of pazopanib versus placebo in patients with soft tissue sarcoma (study excluded patients with GIST or liposarcoma) was initiated in 2008.⁴⁹ 372 patients were registered and 369 were randomly assigned to receive pazopanib (n=246) or placebo (n=123). Median progression-free survival was 4.6 months (95% CI 3.7–4.8) for pazopanib compared with 1.6 months (0.9–1.8) for placebo (hazard ratio [HR] 0.31, 95% CI 0.24–0.40; p<0.0001). Overall survival was 12.5 months (10.6–14.8) with pazopanib versus 10.7 months (8.7–12.8) with placebo (HR 0.86, 0.67–1.11; p=0.25). The most common adverse events were fatigue (60 in the placebo group [49%] vs 155 in the pazopanib group [65%]), diarrhea (20 [16%] vs 138 [58%]), nausea (34 [28%] vs 129 [54%]), weight loss (25 [20%] vs 115 [48%]),

and hypertension (8 [7%] vs 99 [41%]). The median relative dose intensity was 100% for placebo and 96% for pazopanib. Despite improvement in progression-free survival, response rate was only 6% for patients receiving pazopanib.

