10.2 Sample Size and Accrual

A total of 92 evaluable STS patients is required to detect 55% vs 66% with 80% power and an alpha level of 10%. If 32 out of the first 55 patients are alive and progression free at 12 weeks, this trial may enroll up to 108 STS patients in order to accrue a total of 92 evaluable patients. If the trial has not yet achieved 32 responses, may be suspended to enrollment to allow the 55th patient to reach week 12 of treatment for evaluation.

In addition, up to 36 patients with osteosarcoma and 20 patients with liposarcoma will be enrolled to obtain exploratory information for patients with these two histologies. Data exists to help construct baseline event free survival outcomes that can be used as a comparison for future phase II trials for recurrent osteosarcoma ([J Clin Oncol](#). 2016 Sep 1;34(25):3031-8. doi: 10.1200/JCO.2015.65.5381. Epub 2016 Jul 11.)

Using a single arm, 2 stage Phase II trial design: For stage I- If 4 or more of 19 patients have disease control of greater than 4 months then Stage 2 should be opened. The endpoint is that if 11 or more patients/ 36 have disease control at 4 months, then the agent is considered sufficiently efficacious for additional study.

As the study has been using 12 week and 20 week endpoints, we can use 20 weeks instead of 16 weeks as a surrogate endpoint.

The DMC reviewed the interim analysis data on 1/11/2017, and has approved cohort 1 to reopen to 96 total patients(to obtain 92 evaluable patients). In addition, based on the percentage of non-evaluable patients during the interim analysis, it was determined that a total of 108 patients would most likely need to be enrolled in order to obtain 92 evaluable patients.

The remaining slots have been equally divided in 5 ways among the sites, with an expiration date of May 12, 2017. Status of accrual will be reassessed at that time, and the remaining slots will be divided accordingly.

The 16 additional osteosarcoma slots will only be available at Northwestern (NMH).

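### The 55% null rate for pazopanib alone has no stated source and lies below what the cited phase III median suggests, so a pass can reject 55% but does not by itself show improvement over single-agent pazopanib

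*Combined protocol and SAP*

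**What the plan says.** Section 10.1 and the Study Summary describe a single-arm, two-stage test of the 12-week progression-free rate in non-liposarcoma STS (Cohort 1). The null is given as "The historic PD free rate at 12 weeks for single agent pazopanib is 55" percent, with no citation or derivation. The purpose is put this way: "To detect a 20% improvement (an 11% absolute improvement) with the combination of pazopanib and topotecan". Section 10.2 adds: "A total of 92 evaluable STS patients is required to detect 55% vs 66% with 80% power and an alpha level of 10" percent. The test is a "single-arm two-stage optimum design and a one-tailed exact binomial p- value".

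The stage 1 condition is "If 32 out of the first 55 patients are alive and progression free at 12 weeks". The final rule is "if 56 or more out of 92 are alive and progression-free at 12 weeks, then the trial will conclude that the true 12 week PFS"; the value that it goes on to name is 66% or more.

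Section 1.3 has two single-agent pazopanib results. For the phase II study it says that three strata "experienced a 12 week progression free survival rate of" at least 40%, the pre-set activity threshold, and gives no point estimate. For the phase III study, which excluded GIST and liposarcoma, it says: "Median progression-free survival was 4.6 months (95% CI 3.7–4.8) for pazopanib". It gives no 12-week rate. Nothing in the documents reconciles 55% with either study.

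**The concern.** There is no control arm, so the historical rate is the only guard against crediting topotecan with what pazopanib does alone. If the single-agent rate on this endpoint is higher than 55%, the 10% error rate no longer describes the chance of passing an inactive add-on. The cited phase III median points to a higher rate under ordinary curve shapes. At its point estimate with a constant hazard, it gives the same 66% that the trial is powered to detect for the combination. At stake is the claim made after a pass: the plan frames the design as detecting an improvement and then draws a conclusion about a 66% rate.

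**Working it through.** **Inputs.** Null 55%, target 66%, stage 1 rule at least 32 of 55, final rule at least 56 of 92, alpha 10%, power 80%, early termination 63% (section 10.1). Phase III pazopanib median 4.6 months, 95% CI 3.7 to 4.8 (section 1.3).

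**1. The plan's own figures.** The probability of passing with final cut-off c is the sum over x from 32 to 55 of P(Bin(55, p) = x) × P(Bin(37, p) ≥ c − x).

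- Early termination at p = 0.55: P(Bin(55, 0.55) ≤ 31) = 0.631, which matches 63%.
- c = 57: alpha 0.100 and power 0.803, which match the plan.
- c = 56, as printed: alpha 0.136 and power 0.843.

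The stated figures therefore reproduce only with the final count one higher than printed. That is a separate error, worth 13.6 − 10.0 = 3.6 points at a true rate of 55%. Both cut-offs are shown below so that the two effects can be told apart.

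**2. The 12-week rate suggested by the phase III median.** Twelve weeks is 84/30.4375 = 2.760 months. With median m and Weibull shape k, S = 0.5^((2.760/m)^k); k = 1 is a constant hazard.

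| Median (months) | k = 0.5 | k = 0.7 | k = 1 |
|---|---|---|---|
| 3.7 | 0.5^0.864 = 55.0% | 0.5^0.814 = 56.9% | 0.5^0.746 = 59.6% |
| 4.6 | 0.5^0.775 = 58.5% | 0.5^0.699 = 61.6% | 0.5^0.600 = 66.0% |
| 4.8 | – | – | 0.5^0.575 = 67.1% |

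The range is about 55% to 67%, and 55% is at its bottom edge. In the other direction, 55% under a constant hazard means a median of 2.760 × ln 2 / (−ln 0.55) = 3.20 months, below the quoted interval. To have 55% at 12 weeks, the shape must be about 0.29 at a median of 4.6 months, or about 0.50 at 3.7 months.

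**3. Chance of passing if topotecan adds nothing.** The formula in step 1 is evaluated at the pazopanib-alone rate.

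| True rate | Basis | Final count 56 (printed) | Final count 57 |
|---|---|---|---|
| 55.0% | the plan's null | 13.6% | 10.0% |
| 56.9% | 3.7 months, k = 0.7 | 23% | 18% |
| 59.6% | 3.7 months, k = 1 | 41% | 35% |
| 61.6% | 4.6 months, k = 0.7 | 56% | 49% |
| 66.0% | 4.6 months, k = 1 | 84% | 80% |

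**4. What a bare pass supports.** The observed rate at 56 of 92 is 60.9%. The simple exact one-sided 90% lower bound, ignoring the two-stage design, is 53.7%. This does not support a conclusion that the true rate is at least 66%.

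**The case against.** The strongest reply is that the documents contain no phase III 12-week rate. A median of 4.6 months proves only that the rate at 2.76 months is at least 50%; everything above that comes from an assumed curve. A median near its lower limit, combined with steep early loss, brings the rate down to 55%. This stands. A reader might infer that 55% is contradicted by the phase III trial, or that pazopanib alone gives 66%. The documents support neither reading.

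Comparability is also unproven. Cohort 1 excludes further histologies (section 3.2.1), requires one to four prior regimens (3.1.6), counts unequivocal clinical deterioration as progression (2.1), and may drop as non-evaluable, with DMC approval, patients removed before week 12 for reasons other than progression or death (6.3). The documents do not say how the phase III trial handled these matters, so the comparison could shift either way. This also stands, and it is a further reason to justify the null in writing.

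It can be added that any single-arm trial has this limitation, and that the improvement wording belongs to the sample-size rationale while the objective is to determine a rate. That is fair, but the rule goes beyond estimation: it states a conclusion that the data at the pass mark cannot carry.

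A reader might also want a stricter success criterion, such as 68 of 92, so that the exact one-sided 90% lower bound exceeds 66%. The documents do not support that either. It rests on an unseen and rounded 66%, it would be added after the 2017 interim analysis and after accrual closed, and with the same stage 1 rule it would be met with probability only 6.6% at the design's own target of 66%.

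**Conclusion.** The point holds as one of justification and interpretation. The 55% null is the test's only comparator, is unsourced, and lies at the bottom of the roughly 55% to 67% range suggested by the phase III median. Over rates from 56.9% to 66.0%, an add-on with no effect would pass 23% to 84% of the time under the printed rule, or 18% to 80% with 57 as the final count, against a stated 10%. These figures assume Weibull curves with shapes between 0.5 and 1, medians within the quoted interval, and a Cohort 1 comparable with the phase III pazopanib arm. They do not show that 55% is wrong. They show that the error rate depends heavily on an unsupported number, and that a pass supports rejecting 55% or less and no more.

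**What to change.** In section 10.1 and the Study Summary:

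1. Cite the source of 55%. Justify it against the 12-week PFS, with its confidence interval, read from the pazopanib arm of the cited phase III trial, and show the probability of passing over that interval.
2. Replace the conclusion that the true rate is at least 66%. Say instead that a pass rejects a 12-week rate of 55% or less and does not by itself show improvement over single-agent pazopanib. Report the observed 12-week rate with its exact confidence interval beside the phase III rate.

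No new success threshold is needed. The mismatch between final counts of 56 and 57 should be corrected as its own item. The cost is wording and one lookup in a source the protocol already cites; no patients are involved, and the study is already closed to accrual (Appendix H, Amendment 13). The downside is a less favourable claim if the trial passes.
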